Objective	Brief Description/ Justification of Outcome Measure	Outcome Measured By	Time Frame

Assess the effectiveness of NRTS compared to ET on smoking heaviness
	
In addition to assessing the effectiveness of NRTS on abstinence, we want to assess the effect of NRTS on cessation-related behavior including reducing heaviness of smoking.
	
Smoking heaviness indicates cigarettes per day. Timeline follow-back measure of cigarettes per day on each of the past 7 days at 6-months post quit. We will measure cigarettes per day at baseline. We will then compute cigarettes per day at each follow-up timepoint by summing the number of cigarettes each person reports on each day of their follow-up survey and dividing by 7.
	
6 months following baseline.

Assess whether cessation medication utilization mediates the effectiveness of NRTS on 6-month abstinence.
	
Treatment utilization is one mechanism by which NRTS is hypothesized to have its effect.
	
Self-report survey items of use of the nicotine patch and nicotine lozenge at 1-, 3-, and 6- months post baseline. These items will be dichotomized as used NRT vs. hasn't used NRT in the 6 months post intervention. In addition, days of NRT use will be computed.
	
6-months following baseline.

Objective	Brief Description/ Justification of Outcome Measure	Outcome Measured By	Time Frame

Assess whether attitudes towards NRT (safety and efficacy) mediate the effectiveness of NRTS on 6-month abstinence.
	
We hypothesize that one mechanism of action of NRTS is to cause more favorable attitudes towards NRT.
	
Self-report survey items at baseline, 1-month, 3-month and 6-month surveys of perceptions of nicotine replacement therapy safety and efficacy. We will assess perceptions of NRT efficacy on a 5-point Likert-scale where higher scores indicate greater efficacy. We will assess safety with a single item measure on a 5-point Likert scale where higher scores indicate greater perceptions of NRT safety.
	
6-months following baseline.

Objective	Brief Description/ Justification of Outcome Measure	Outcome Measured By	Time Frame

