9.1.2 Baseline survey (day 0; in dental practice)

The baseline survey will be administered prior to the intervention. It includes the following measures:

- Contact information
- Demographics (biological sex, gender, ethnicity, race, age)
- Toothbrushing habits
- Smoking history (cigarettes per day, time to first cigarette in the morning, previous quit attempts, past cessation treatment)
- Interest in quitting
- Confidence to quit
- Attitudes about nicotine replacement therapy

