9.1.3 After visit survey (Target day 0, in dental practice or remotely)

Following the dental visit, participants will be sent a link via email or text with an after-visit survey. If participants do not respond to the survey within 3 days, they will receive a phone call from Hennepin Healthcare study staff. They will be paid \$20 for after visit survey completion.

The after-visit survey will assess the following:

- the elements of ask-advise-refer as a fidelity check (asked about smoking, advised to quit, asked about interest in quitting, discussed medications, advised to use medication, provided with medication, referred to quit line)
- Demographics (educational attainment, urban/suburban/rural community, zip code, number in household, income, health insurance, dental insurance)
- oral health status
- relationship with dentist
- other non-cigarette tobacco product use
- acceptability of the intervention

9.1.4 1-month follow-up survey (target day 30, conducted remotely)

The one-month follow-up survey will be conducted via email or text. Participants who do not respond will be followed up by phone and/or mail. Participants will be paid \$20 for survey completion.

The one-month follow-up survey will assess the following:

- smoking behavior (smoking each day for the past 7 days, date of last cigarette)
- use of other tobacco products (electronic cigarettes, hookah, cigars, chewing tobacco, snus, pipes, other)
- quit attempts
- use of nicotine patch and lozenge (including sample patches and patches purchased outside of study; use in past 7 days, ever use)
- reasons for nicotine patch/lozenge use
- perceived patch/lozenge effectiveness
- enjoyment of patch/lozenge
- use/purchase of smoking cessation medications,
- use of smoking cessation counseling
- patch/lozenge side effects (nausea, headache, heartburn, mouth soreness, dizziness, dry mouth, sore jaw, excessive salivation, insomnia, hiccups, burning in throat/mouth, skin irritation, skin redness, skin itchiness)

- belief that side effects were caused by patch/lozenge
- perceived oral health status
- frequency of toothbrushing
- type of toothbrush
- interest in stopping smoking
- readiness to quit
- attitudes about nicotine patch, lozenges.

9.1.5 3-month follow-up survey (Target day 90, conducted remotely)

The 3-month follow-up survey will be conducted via email or text. Participants who do not respond will be followed up by phone and/or mail. Participants will be paid \$20 for survey completion.

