12.1 Study Hypotheses

Hypothesis 1 (primary): Participants receiving the NRTS intervention will have a higher frequency of biochemically confirmed abstinence at 6 months post enrollment compared to ET.

Hypothesis 2a: Participants receiving NRTS will be more likely to have a 24-hour quit attempt than ET.

Hypothesis 2b: Participants receiving NRTS will have greater reductions in smoking heaviness compared to baseline than ET.

Hypothesis 3a: Use of nicotine replacement therapy (patch and lozenge) will mediate the effect of NRTS on biochemically confirmed abstinence at 6 months post enrollment.

Hypothesis 3b: Perceptions of NRT safety and efficacy will mediate the effect of NRTS on biochemically confirmed abstinence at 6 months post enrollment.

Hypothesis 3c: Intention to use NRT will mediate the effect of NRTS on biochemically confirmed abstinence at 6 months post enrollment.

Hypothesis 3d: Intention to quit smoking will mediate the effect of NRTS on biochemically confirmed abstinence at 6 months post enrollment.

Hypothesis 4a: NRTS will be considered feasible to administer in dental settings.

Hypothesis 4b: NRTS will be acceptable to practitioners and patients.

Hypothesis 5: NRTS will be cost effective.

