To test hypothesis 1, we will compare treatment groups with respect to the primary outcome (biologically verified 7-day PPA from use of combusted tobacco at six months) using generalized hierarchical linear modeling⁴³⁻⁴⁵ with a binomial distribution and logit link (aka mixed effects logistic regression) that account for the clustering of individual observations within dental practice, while adjusting for various patient and practice related factors.^{46,47} The first level of the model (participant) will include any individual level covariates. The second level of the model will include the fixed effects for treatment group (ET=0, NRTS=1) and the cluster level stratification factors and a random effect for the participant level intercept. A significant coefficient for the treatment group indicator with an odds ratio > 1 would provide support for the effectiveness of NRTS on smoking abstinence at 6 months.

This same model framework will be used to examine the secondary outcomes of abstinence at 1 month and abstinence at 3 months and whether there was a quit attempt at 1,3, or 6 months. To determine whether the intervention had an effect on smoking heaviness over time, we will use a three-level hierarchical linear model that will account for the nesting of observations within persons and persons nested within practices. The first level of the model will include a categorical fixed effect for time (baseline [reference group], 1 month, 3 month, 6 month). The second level of the model will include fixed effect for any individual level covariates and random coefficient for the level 1 intercept. The third level will include for treatment group and the cluster level stratification factors and a random effect for the participant level intercept, including the terms for the time vectors representing the cross-level interactions. Significant terms for the cross-level interaction would indicate that the change in smoking heaviness differed

by treatment group, and will be followed up with examination and plots of the estimated marginal means do determine whether those in the NRTS group had greater decreases in smoking heaviness compared to the ET group.

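### Smoking heaviness comes from different measures at baseline and follow-up, yet baseline is modelled as the reference occasion of one outcome, so within-arm decreases mix instrument change with behaviour change

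*Protocol*

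**What the plan says.** **Baseline.** The outcome table in 4.2 says only "We will measure cigarettes per day at baseline". The survey content in 9.1.2 places it under "Smoking history (cigarettes per day, time to first cigarette in the morning, previous quit attempts, past cessation treatment". No 7-day timeline follow-back is listed there, and neither the item's wording nor its recall window is given.

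**Follow-up.** The table in 4.2 describes a "Timeline follow-back measure of cigarettes per day on each of the past 7 days at 6-months post quit", scored "by summing the number of cigarettes each person reports on each day of their follow-up survey and dividing by 7". The survey lists for 1, 3 and 6 months (9.1.4 and the two sections numbered 9.1.5) carry the matching item, "smoking behavior (smoking each day for the past 7 days, date of last cigarette".

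**Hypothesis 2b (12.1).** "Participants receiving NRTS will have greater reductions in smoking heaviness compared to baseline than ET".

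**Analysis (12.3).** A three-level linear model has a "categorical fixed effect for time (baseline [reference group], 1 month, 3 month, 6 month", with arm-by-time terms. "Significant terms for the cross-level interaction would indicate that the change in smoking heaviness differed" by arm, and estimated marginal means are then examined and plotted to see whether decreases were larger under NRTS.

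The protocol gives no mean, standard deviation, effect size or power for cigarettes per day. The power section (12.2) is confined to the primary outcome.

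**The concern.** A model with baseline as the reference level of time assumes that every occasion measures the same quantity on the same scale. As described, baseline is a general cigarettes-per-day figure and follow-up is the mean of seven daily reports, smoke-free days included. Any systematic gap between them enters every time term and shows up as change in smoking.

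Three things are at stake: whether a plotted decrease can be read as behaviour change, whether the arm contrast is in the units that Hypothesis 2b implies, and how precisely that contrast is estimated. A smaller matter is the fixed divisor of 7, which behaves badly if a record with unanswered days is ever scored.

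**Working it through.** There is no protocol figure to reproduce here, so the numbers below illustrate assumed values.

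**1. What cancels and what does not.** Let B be mean cigarettes per day on the baseline measure, and F the follow-up mean as that same measure would have read it. Suppose the follow-up instrument reads a + s·F, with a and s equal in both arms.

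- Within-arm change = a + s·F - B. It contains both a and s.
- Arm contrast = s·(F_NRTS - F_ET) - (B_NRTS - B_ET). The shift a cancels; the factor s does not.
- With a chance baseline imbalance d and a true effect Δ, the contrast is s·Δ - (1 - s)·d.

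**2. Size.** Assumed: baseline mean 15, SD 6, and true changes of about -1.0 (ET) and -2.5 (NRTS). Truncating negative values at zero makes the simulated NRTS change -2.48 and the contrast -1.48.

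| Scenario | Change, ET | Change, NRTS | Arm contrast |
|---|---|---|---|
| Same instrument | -1.00 | -2.48 | -1.48 |
| Shift of -2 in both arms | -3.00 | -4.48 | -1.48 |
| Scale factor 0.85 in both arms | -3.11 | -4.36 | -1.25 |

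The third contrast agrees with 0.85 × -1.48 = -1.26 up to simulation error. For the imbalance term, d = 1 cigarette per day with s = 0.85 adds -(0.15)(1) = -0.15.

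**3. Is a scale factor near 0.85 possible?** Section 6.1 admits patients who smoke on 25 days a month. Assume a 30-day month and a baseline answer given per smoking day. A patient at that boundary then averages 7 × 25/30 = 5.83 smoking days a week, so the 7-day mean is 25/30 = 0.833 of the baseline answer, 16.7% lower with no change in behaviour. A daily smoker has a factor of 1. From this source alone 0.85 is therefore near the extreme.

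**4. Precision.** With equal variances σ² on both occasions, correlation rho and complete data, the variance per person is 2(1 - rho)σ² for a change and (1 - rho²)σ² after baseline adjustment. The ratio is 2/(1 + rho): 1.33 at 0.5, 1.25 at 0.6 and 1.18 at 0.7.

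This ignores clustering. A practice effect that is constant over time cancels from a change but not from a follow-up mean. Suppose the ICC of 0.013 in 12.2, which is for abstinence, also held for cigarettes per day, with 24 patients per practice. The correlation between practice means is then (rho + 23 × 0.013)/(1 + 23 × 0.013) = (rho + 0.299)/1.299, that is 0.615 at rho 0.5 and 0.769 at rho 0.7. The ratio 2/(1 + r) falls to 1.24 and 1.13. The loss shrinks but stays.

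**5. Fixed divisor.** If a constant smoker of c per day leaves k days unanswered and the record is scored, the result is c(7 - k)/7. For c = 15 that is 12.86, 10.71 and 8.57 at k = 1, 2 and 3: apparent falls of 14.3%, 28.6% and 42.9%. In the setting of step 2, 5% unanswered days in both arms gives a contrast of -1.41. Rates of 5% (ET) and 10% (NRTS) give -2.04, and 10% and 5% give -0.70.

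**The case against.** **The test is comparative.** Hypothesis 2b is judged by the arm-by-time interaction. A reader might infer that its test is biased by the change of instrument. The documents do not support that: an additive shift common to both arms leaves the contrast at -1.48, and nothing suggests that the instruments would behave differently by arm. This part of the objection stands. What remains is the within-arm reading and the scale factor. Even the scale effect is partly a matter of units: with balanced baselines, the contrast is simply a difference in 7-day means, not in baseline units.

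**The baseline list names topics, not items.** The baseline question could be closer to the follow-up one than it looks, and calling it a single item would be an inference. That stands as a caution. Still, the same protocol lists a day-by-day item at all three follow-ups and none at baseline.

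**Participants smoke almost daily at entry.** The protocol summary describes daily smokers, so smoke-free days at baseline are few and a factor far below 1 is unlikely from that source. This stands. Smoke-free days at follow-up may also be genuine change.

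**The variance ratio is not a cost of the mismatch.** Correct: it applies with identical instruments too, and it rests on the simplifications in step 4. It argues about how baseline is used, not about the instruments.

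**Blank days.** A reader might infer that the protocol counts unanswered days as zero, or that patients keep a diary. Neither is written. The instrument is a survey timeline follow-back, no rule for partial records is given, and section 14 describes validated data entry, which may prevent blanks. A statistical analysis plan could settle the scoring. However, 6.3 allows a paper survey, on which blanks are possible, and the fixed divisor is already stated.

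**Conclusion.** The point holds in limited form. As described, baseline and follow-up heaviness come from different measures while 12.3 treats them as occasions of one outcome, so within-arm decreases shown as marginal means cannot be read as behaviour change alone. The arm contrast is unaffected by a common additive shift. It is rescaled by a common scale factor (about -1.25 instead of -1.48 at an assumed 0.85) and picks up a small term if the arms differ at baseline.

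Separately, the unconstrained baseline row costs precision: a variance ratio of 1.18 to 1.33 for an assumed rho of 0.7 to 0.5, or 1.13 to 1.24 if the abstinence ICC is carried over. The fixed divisor understates smoking only if partly answered records are scored, and biases the arms materially only if completeness differs between them.

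All magnitudes rest on assumed values. This is a secondary outcome; the primary outcome and Table 11.1 are untouched.

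**What to change.** Either of two changes removes the mismatch:

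1. Add the same 7-day cigarette items to the baseline tablet survey (9.1.2), so that all four occasions share one scale. This costs seven short entries per patient. It does not by itself recover the precision in step 4; baseline would still need to enter as a covariate.
2. Keep the baseline item, take it out of the outcome, model only the 1-, 3- and 6-month values with baseline cigarettes per day as a covariate, and report arm differences instead of within-arm reductions. This costs revised wording in 12.3, with Hypothesis 2b phrased to match. It is the only route for patients already enrolled without a 7-day baseline record.

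Under either route, amend 4.2 to divide by the number of days answered, with a stated minimum below which the record is treated as missing.

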5 STUDY DESIGN

Study design. This is a 2-arm, phase 2, cluster randomized effectiveness clinical trial that will be conducted in the National Dental PBRN, which is a network of participating dental practitioners who conduct practice-based oral health research. This study will utilize the resources of the ARC and NCC. The node coordinators will utilize ARC's established communication methods to inform prospective dental practitioners about the study opportunity. Enrolled practitioners will recruit and enroll patients during routine dental care appointments.

Study Population: The practitioner study population will include National Dental PBRN practitioners, dental therapists and hygienists. We will enroll approximately 50 practices across the Midwest and Northeast Regions of the PBRN. Each practice will recruit approximately 24 patients for a patient population of 1200.

Means of Data Collection: Data collection will be centralized. Survey data will be collected using the REDCap platform administered by the NCC. CO data will be collected via the iCO quit personal CO monitor. The iCO quit devices will be mailed to participants who will take the test using an app downloaded to their smartphone. Interviews will be completed by phone and audiorecorded.

Interview. Following a practitioner's participation in the trial, we will conduct stakeholder interviews with 10-12 dentists, 10-12 other staff, and 10-12 patients. Topics include patient and practitioner experiences with the intervention, provider perceptions of barriers and facilitators to adoption and tools/supports/structures needed for implementation.

Collection Timeframe: Following screening and consent, patient data will be collected at 5 timepoints, baseline, immediately following the baseline visit, and target of 1 month, 3 months, and 6 months following the visit. For practitioners, data collection will occur prior to initiation of site data collection and following completion of site data collection.

6 STUDY POPULATION

6.1 Participant Inclusion Criteria

In order to be eligible to participate in this study, a practitioner must be a National Dental PBRN practitioner who meet the following criteria:

- Willing to consent patients to the study following regionally approved procedures
- Is expected to remain in the practice for the 1-year study duration and agrees to collect participant research data
- Verbally affirms that the practice can devote sufficient time in patient scheduling to allow focused recording of all data required for the study. Study activities take approximately 20-25 mins per participant.
- Does not anticipate retiring, selling the practice or moving during the study
- Is affiliated with the National Dental PBRN or is willing to affiliate with the National Dental PBRN in order to participate in the study.

In order to be eligible to participate in this study, a patient must meet all of the following criteria:

- Provide a signed and dated informed consent form
- Willing to comply with all study procedures and be available for the duration of the study
- Age ≥ 18 (except in Nebraska where age of consent is ≥ 19 years)
- Smokes at least 1 combustible cigarette per day 25 days/month
- Willing to receive texts and emails from the study

6.2 Participant Exclusion Criteria

A patient who meets any of the following criteria will be excluded from participation in this study:

- Does not own a smart phone with internet access
- Unwilling or unable to provide informed consent
- Myocardial infarction or stroke in the past 3 months
- Pregnant or breastfeeding
- Use of tobacco cessation medication in the past week
- Previously enrolled in the study

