	
post enrollment
 
 2. Cigarettes per day in the 6 months post enrollment 
3. Assess whether nicotine replacement therapy utilization, attitudes toward NRT, intention to use NRT, and intention to quit smoking mediate the effect of the intervention on abstinence
 
Mediators:
 
 1. Use of Nicotine patch or nicotine lozenge 2. Attitudes towards NRT (safety and efficacy) 3. Intention to use NRT 4. Intention to quit smoking 
4. Assess intervention feasibility and acceptability. Conduct a multi-stakeholder process evaluation of the NRTS intervention to aid future implementation through a multi-stakeholder process evaluation.
 
Outcomes:
 
 1. Acceptability of NRTS 2. Feasibility of NRTS 
5. Assess the cost effectiveness of the NRTS intervention.
 
Outcomes:
 
 1. Cost per quit 2. Cost per quality adjusted life year

Population:
	
Target of 50 National Dental PBRN practices and 1200 patients who smoke combustible cigarettes in PBRN practices
 
Gender: Males, Females, non-binary
 
Age range: 18-No limit (except in Nebraska where consent is age ≥ 19 years)
 
Demographic group: National Dental PBRN practitioners and their patients who smoke cigarettes daily, own a smart phone with reliable Internet Access, are willing to receive study emails

	and texts, are free of contraindications to NRT and who have not used tobacco cessation medications in the past week.
Phase or Stage:	phase 2
Number of Sites:	Approximately 50 practices across the Midwest and Northeast National Dental PBRN regional nodes.
Description of Intervention:	2-week supply of 14mg transdermal nicotine patches and a 2-week supply of 4mg nicotine lozenges
Study Duration:	Approximately 3 years, includes ramp-up period (6 months), full-scale trial (2 years), interviews following trial participation, data synthesis and manuscript preparation.
Subject Participation Duration:	Patient participant duration: 6 months Practitioner expected duration to recruit approximately 24 patients: 1 year
Estimated Time to Complete Enrollment:	18 months

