Specific risks of using nicotine lozenge. The most common adverse effects of using nicotine lozenge are nausea/GI upset, mouth/throat irritation, and hiccups. In previous studies of lozenge, drop-out due to AEs were very low (<10%) and SAEs have been reported in <2% of the sample (with no deaths or irreversible injuries attributed to lozenge use) and have not differed between lozenge and placebo.^{33–35}

Specific Risks of using nicotine patch. The most common adverse effects of using nicotine patch include local skin irritation at the site of the patch, disturbed sleep and vivid dreams, headache, and nausea. Less common are allergic skin reactions to the patch. In a recent trial,³³ 7% of participants discontinued patch use due to adverse events.

Specific risks of using nicotine patch and nicotine lozenge concurrently. Our sampling intervention allows smokers to briefly try both nicotine patch and nicotine lozenge, either singularly or concurrently. We will not explicitly encourage dual use, but we will not discourage it either. Combination treatments are often suggested for more dependent smokers and/or smokers with chronic medical conditions.^{36–38} In a recent trial of placebo vs. single vs. multiple medications for smoking cessation,³³ the four most common adverse events within the combined patch/lozenge group (n = 262) were: 1) disturbed sleep: 9.0%, compared to 5.6% in placebo group, and 2) skin irritation: 8.9%, compared to 2.7% in placebo group, 3) nausea: 7.9%, compared to 4.4% in placebo group, and 4) mouth/throat irritation: 5.7%, compared to 3.3% in placebo group. All other adverse events occurred <5%.

Risks of medication being used by a person other than the participant. Nicotine replacement therapy is available over the counter and as such, risks of use by someone other than the participant are similarly low as those of the participant. Nicotine replacement therapy products should not be used by children.

Minimization of risks of using NRT. The primary protection against risks of using nicotine patch and nicotine lozenge (both OTC products) is the short duration for which they will be provided— only a 2-week supply. The packet of print materials that participants will receive includes FDA package instructions and a supplemental handout

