with instructions on how to minimize side effects including moving the site of nicotine patch placement each day and not repeating site of use for at least one week to minimize the risk of skin irritation. Also, participants will be instructed to remove the patch before bed if it significantly interferes with sleep. Finally, these materials will discuss anticipated negative consequences of dual use (nausea, headache) and advise participants to discontinue one or both products should they arise. To reduce the risks of medications being given to those other than study participants, we will instruct participants upon distribution of samples not to give medication to others. Medication packages will also have a sticker that says “for FreSH participant use only- do not distribute.” Medication comes in childproof packaging.

Our Data and Safety Monitoring Plan includes monitoring of Adverse Events (AEs). We will exclude patients based on standard FDA contraindications for NRT use (pregnancy, recent cardiovascular trauma). We will clearly advise against use of NRT during pregnancy and breastfeeding and will exclude patients who report that they are pregnant or breastfeeding. As part of routine dental visits, patients are asked about their pregnancy status, as some dental procedures and medications are contraindicated for pregnant women. A physician will be available throughout the study for consultation about AEs, etc. Participants will be instructed to discontinue use of the patch and/or lozenge entirely if a severe reaction develops. They will be encouraged to contact the research team (not their dentist) as soon as possible if they experience a SAE or if they have a reaction for which OTC labeling suggests seeing a provider. In the AAR training, dentists will get training on how to manage adverse events of NRT. However, for this study, participants and dentists will be advised that the study team, not the dentist, is responsible for managing study-related AEs. We will advise patients who have a study-related SAE to discontinue use of the study treatment (NRT or ET). Following any AEs or SAEs, if the study physician, the participant’s personal physician or the participant wishes it, the participant will be withdrawn from the study.

Risks of using NRT concurrently with cigarettes and/or other tobacco products

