7.4 Study Behavioral Intervention Description

Practices will be randomly assigned to study condition (NRTS or ET). Practices will be instructed not to disclose the intervention condition to the patient participant until after the baseline survey has been completed.

AAR (both conditions): Practitioners (NRTS and ET) will be encouraged to deliver AAR to all patients regardless of trial participation.

Patient participants will receive:

- monogrammed study bag
- study trinkets such as pens and post-it notes
- a brochure published by the ADA describing the effects of tobacco use on oral and general health
- contact information for their state tobacco quitline
- information about tobacco cessation medications
- study contact information
- the follow-up schedule
- condition specific information about NRT/ET
- consent form
- HIPAA form

NRT sampling (NRTS): Practices assigned to NRTS will dispense NRT samples in addition to AAR.

Patient participants will receive: a “starter pack” consisting of a 2-week supply of both nicotine patches (14 mg) and lozenges (4 mg; combination NRT [C-NRT]). Practitioners will spend 1-3 minutes on instruction prior to dispensing samples. Instructions for NRT use are provided on each medication package. We will also include FAQs and information dispelling misconceptions. Practitioners will neither explicitly advise nor discourage combined use or concomitant use with cigarettes. Patients will receive oral and written instructions including how to obtain more nicotine replacement therapy if interested (e.g., from their primary care provider, or purchased over the counter). Practitioners will instruct patients that the samples are an opportunity for smokers to learn about two NRT products that can be used individually or together (participant choice, including none at all). Some suggested uses could be:

- to get experience with the products and determine if they like them
- to reduce smoking or restrict where they smoke

- to make a practice quit attempt
- to get started on quitting

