8.2 Screening/Enrollment/Baseline/study intervention

Visit 1, Day 0

- Practitioner Reviews dental record to determine eligibility criteria
- Practitioner verifies inclusion/exclusion criteria via an electronic screening questionnaire taken by the participant
- Practitioner obtains and documents consent from participant with electronic consent or paper consent. Participants will digitally sign the consent form if offered electronically, and will sign paper consent forms if a paper version is used.
- Participant completes contact information form
- Participant completes baseline survey
- Practitioner provides study intervention

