9 STUDY PROCEDURES/EVALUATIONS

9.1 Study Procedures/Evaluations

9.1.1 Screening and enrollment (day 0; in dental practice)

- Participants will be enrolled during a routine dental visit at their general practice dental provider's office. Patients who smoke combustible cigarettes will be offered the study.
- Interested participants will complete a screening assessment via REDCap on tablet or via a link texted or emailed to their phone. The self-report eligibility screen includes age, smoking status, smartphone ownership, medical contraindications to NRT (pregnancy, breastfeeding, recent heart attack or stroke), and smoking cessation medication use in the past week (any use of nicotine replacement therapy [patch, gum, inhaler, lozenge, nasal spray], any use of Chantix/varenicline, use of bupropion/zyban/Wellbutrin for the purpose of quitting smoking).
- Finally, interested and eligible participants will complete an electronic written informed consent via REDCap or will complete a paper consent form. If required a HIPAA form will be completed on paper or electronically (depending on the regional IRB rules).

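### Neither the eligibility screen (6.2, 9.1.1) nor the dispensing steps in 7.4 ask about an earlier allergic or severe reaction to the nicotine patch or lozenge: a minor safety gap in the NRTS arm

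*Protocol*

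**What the plan says.** **Risk and stop rule (3.3.1).** Among the patch risks the protocol writes: "Less common are allergic skin reactions to the patch". Among the risk-minimisation steps it writes: "Participants will be instructed to discontinue use of the patch and/or lozenge entirely if a severe reaction develops". Section 6.5.2 repeats the stop instruction.

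**Eligibility.** The six exclusions in 6.2 are: no smartphone with internet access, no informed consent, heart attack or stroke within 3 months, pregnancy or breastfeeding, "Use of tobacco cessation medication in the past week", and earlier enrolment in the study. Section 3.3.1 gives the basis for the medical ones: "We will exclude patients based on standard FDA contraindications for NRT use (pregnancy, recent cardiovascular trauma"). The tablet screen in 9.1.1 covers "medical contraindications to NRT (pregnancy, breastfeeding, recent heart attack or stroke") together with recent cessation medication. The Protocol Summary describes the population in general terms as patients who "are free of contraindications to NRT and who have not used tobacco cessation medications in the past week". At Visit 1 (8.2), "Practitioner Reviews dental record to determine eligibility criteria".

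**Dispensing.** Section 7.4 states: "Practitioners will spend 1-3 minutes on instruction prior to dispensing samples". It describes the content of that instruction: how the products may be used, that they may be used singly, together or not at all, and where to get more. It mentions no question about earlier reactions.

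**The concern.** The protocol recognises a reaction serious enough to end use of a product, but asks about it only once it has happened in the trial. A patient who had such a reaction to a patch a year ago passes every listed criterion and is given a two-week supply of both products. Patients with past exposure are to be expected: the exclusion reaches back only one week, and the baseline survey itself records past cessation treatment. What is at stake is an avoidable repeat reaction in a small number of NRTS patients. Patients in toothbrush (ET) practices receive no nicotine product and are not exposed. Nothing in the estimate of abstinence or its test depends on this point.

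**Working it through.** No figure in the protocol bears on the gap itself, so the check is a reading of every place where a question about earlier reactions could sit.

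1. **6.2, exclusions.** Two medical items (recent heart attack or stroke; pregnancy or breastfeeding) and one medication item limited to the past week. None concerns tolerability.
2. **9.1.1, self-report screen.** The contraindications are itemised in brackets: pregnancy, breastfeeding, recent heart attack or stroke. Allergy and prior reaction are absent.
3. **Protocol Summary, Population.** Freedom from contraindications could be read broadly, but 3.3.1 and 9.1.1 both spell out what is meant, and neither list includes allergy.
4. **8.2, dental record review.** The practitioner checks the record against the eligibility criteria. With no criterion on reactions, a noted allergy gives no protocol ground to act.
5. **9.1.2, baseline survey.** It records past cessation treatment but lists no item on reactions, and it is not an eligibility check.
6. **7.4, dispensing.** The described instruction contains no such question.
7. **Safeguards that do exist.** FDA inserts with both products (7.1.2); a handout on side effects, practitioner training on adverse events and a physician for consultation (3.3.1); use of either product at the patient's choice (7.4). These inform the patient or respond to an event. None is described as asking about the past before dispensing.

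**What a trial-wide exclusion would cost.** This is the obvious alternative remedy, so its price is worth showing. The base case in Table 11.1 has ICC 0.013, 25 practices per arm, 24 patients per practice, and 5.5% against 10.5% abstinent.

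- Design effect = 1 + 23 × 0.013 = 1.299; effective n per arm = 600 / 1.299 = 461.9.
- SE = √[(0.055 × 0.945 + 0.105 × 0.895) / 461.9] = 0.01778.
- Power = Φ(0.05 / 0.01778 − 1.96) = 80.3%, which matches the table.
- If an assumed 1% (12 of 1200) were screened out and not replaced: 23.76 per practice, design effect 1.2959, effective n 458.4, power 80.0%. At an assumed 0.5% it is 80.2%, and at 2% it is 79.7%.

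These figures price that remedy only. They do not measure the gap.

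**The case against.** The best case against is that nothing here is stated wrongly. The contraindication lists in 3.3.1, 6.2 and 9.1.1 agree in leaving allergy out, and 3.3.1 never promises to exclude allergic patients. Naming a risk does not oblige a trial to make it an exclusion. The stop rule concerns a reaction that arises during use, and it stops the product, not participation: 6.5.1 lets participants leave the intervention and still be followed. Being handed an over-the-counter product is not the same as using it. Broad eligibility and uniform dosing are deliberate in this effectiveness trial.

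Most of that stands, and it rules out several stronger readings that a reader might infer:

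- *That the protocol contradicts itself.* It does not; its sections are consistent on this point.
- *That 6.2 is defective and must exclude these patients.* A trial-wide exclusion would remove ET patients who receive no nicotine, and NRTS patients who could use the other product.
- *That the list misstates the FDA contraindications.* The labels are not in the documents, so this cannot be judged.
- *That lozenge allergy is a documented risk.* Section 3.3.1 names allergic reactions for the patch only; for the lozenge it lists stomach upset, mouth or throat irritation and hiccups.
- *That the 7% patch discontinuation quoted from one trial in 3.3.1 sizes the problem.* That figure covers all adverse events, not allergy.

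What does not stand is the inference that nothing need change. Consistency among the lists does not supply the missing question, and the existing safeguards are not described as asking it before the product leaves the practitioner's hands.

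**Conclusion.** The gap is real and minor. It is a safety matter for the NRTS arm alone, with no bearing on the primary analysis or on power. Few patients are likely to be affected. The number cannot be estimated, because the documents give neither lifetime use of patch or lozenge in this population nor the rate of allergic or severe reactions.

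The conclusion rests on one assumption: that the full dispensing script and quick guide, which are not reproduced in the protocol, add no such question beyond what 7.4 and 9.1.2 describe. The consent pages were also not available. If those materials already ask, the remaining task is only to record the step in 7.4.

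**What to change.** Leave 6.2 and the 9.1.1 screen unchanged. In the NRTS dispensing script (7.4) add:

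- a question on whether the patient has ever had an allergic or severe reaction to a nicotine patch or, as a precaution, to a nicotine lozenge;
- the instruction *Do not use a product you have had an allergic or severe reaction to*;
- a direction to give only the other product where the answer is yes for one of them.

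This fits the existing message that the products may be used individually or not at all. The question comes after consent and the baseline survey, so it cannot alter who enters the trial, and eligibility stays identical in NRTS and ET practices. The patient remains enrolled, followed and analysed in the NRTS arm. Any product withheld should be recorded, so that the fidelity check in the after-visit survey does not count it as a failure to deliver the sample.

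The cost is a few seconds of practitioner time and single-IRB review of the amendment. No participant is lost. Because the answer is self-reported, the change lowers the risk but does not remove it.
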